## **VII. RISKS AND DISCOMFORTS**

**a. Complications of surgical and non-surgical procedures**

There are no surgical procedures as part of this study. Given that participants do not need to physically come to the hospital to participate in any study procedures, there is no risk of physical injury to participants.

The process of collecting a dried blood spot sample is relatively painless and non-invasive; however, participants may face minimal discomfort when completing this procedure. Prior to the dried blood spot sample collection, participants will be informed that the procedure may involve mild, temporary pain at the finger prick site and will be provided with suggestions for minimizing any pain that is bothersome (e.g., putting ice on the site). Participants will be sufficiently trained by study staff in how to self-collect their blood samples at home. Participants will be given the option to opt out of any dried blood spot collection points, for any reason. Participants who oppose the provision of dried blood samples will not be

excluded from additional study procedures. In our previous study, it was common for ACS patients to already have experience using the blood spot finger-prick technique for their healthcare and almost all participants expressed comfort and willingness to complete this procedure as part of a research study.

**b. Drug side effects and toxicities**

There are no drug side effects or toxicities associated with this study.

**c. Device complications and malfunctions**

There are no risks of device complications.

**d. Psychosocial risks**

Patients may experience discomfort from completing the survey questionnaires or exit interview and/or participating in the intervention mindfulness trainings or discussions. Participants who do not find the study to provide a benefit to them may find this upsetting as well. All possible measures will be taken to ensure patient comfort and participants will be informed that they could exit the study at any point with no penalty. The PI (licensed clinical psychology) will be available while intervention groups are being conducted to intervene if needed (due to patient discomfort or to answer specific questions about the study). Participants will be informed that they can choose not to complete any surveys or answer any specific survey items or exit interview questions that make them feel uncomfortable, and that they do not need to complete the blood spot procedures. All of these procedures are consistent with sound research design and do not unnecessarily expose subjects to risk.

The main psychosocial safety concern related to patients in this study is worsening depression symptoms and/or suicidal ideation. Subject safety regarding mood and suicidal ideation will be ensured in several ways.

First, eligibility criteria require that patients do not have active suicidal ideation at the time of enrollment, and that they have not been hospitalized for a psychiatric reason in the past year. Thus, it is not likely that participants will report active suicidal ideation during or following the intervention. Moreover, our eligibility criteria require only minimal depression symptoms and thus we do not expect to have a severely depressed sample.

During the eligibility screening procedures, participants will be administered the Patient Health Questionnaire-9 (PH-9) over the phone. If any patient endorses suicidality (i.e., PHQ-9 item 9 score above 0; “Over the past two weeks, how often have you been bothered by thoughts that you were better off dead or of hurting yourself in some way”), the RA will follow our standardized safety assessment protocol that our team has developed and used in prior funded studies of ACS patients with elevated depression symptoms. The protocol involves further assessing safety risks through a series of structured questions, with

specific instructions at each step based on the patients' response. It begins by clarifying the response to PHQ-9 item 9 (i.e., determining passive versus active suicidality). If patients endorse active suicidality, the RA will further assess safety risks (e.g., plan, intent, past suicide attempts) and immediately notify the PI (a licensed clinical psychologist) to conduct further assessment. The PI will conduct detailed suicide assessment of patients with active suicidality and inform the patient's primary treatment providers of the patient's symptoms and assist with the obtainment of further evaluation and care as needed (e.g., through referral to outpatient treatment or to the emergency department [ED]), depending on the urgency of the situation. In our previous work, it has been extremely rare for an ACS patient to report active suicidality that requires intervention.

Upon enrollment, the RA will also conduct proactive safety planning with all participants in the following ways: (1) asking participants to identify 1-2 safety contacts that we would contact in the event that participants become at risk, (2) working with participants to identify the emergency department nearest to their home; (3) and instructing patients to go to this emergency room if they feel unsafe, and inform research staff once they are in a safe place (e.g., hospitalized or back at home). Participants will be asked to report any worsening symptoms to the interventionist during sessions, or in between sessions by contacting the study RA.

For enrolled participants, the PHQ-9 will be administered at baseline, post-intervention, and 3-month follow-up, which will allow us to monitor for worsening depression symptoms. The RA will review changes in participant's PHQ-9 scores over time and contact the participant to discuss any concerns, asking about their symptoms, needs, and concerns about staying in the study, and conducting an initial safety assessment as needed (as described above). The same procedures as described above will be followed if participants endorse suicidality on PHQ-9 item 9 when completing the measure as part of any of the surveys. REDCap will be set up to send automatic alerts to the study staff for any PHQ-9 item 9 responses greater than zero. Participants will be contacted within 24 hours.

The interventionists for each group will observationally monitor participant's symptoms during each weekly intervention session. If the interventionists become concerned based on a participant's presentation during a session (e.g., per their clinical observation or expressed SI by a participant), they will call the participant by phone individually immediately after the session to check in about the participant's symptoms and conduct a safety assessment if needed (following the protocol outlined above). The interventionist will be a licensed mental health provider trained in conducting safety assessments. Interventionists will instruct patients at the start of the first session that if they experience suicidal thoughts or worsening depression symptoms at any point during the study, they should let the interventionist, study staff, and/or their doctors know.

The objective criteria for removal from the study is worsening psychiatric symptoms that become psychiatrically unstable that precludes their participation (e.g., constitute danger to self or others). The RA and interventionist will inform the PI of any concerns about a participant's symptoms and about any contact with participants regarding these concerns. They will let the participants know that if it seems unsafe for them to remain in the study, the PI will contact them. In cases where depression symptoms are worsening but do not constitute necessary removal from the study, the PI will discuss the concerns with the participant, give them the option to exit the study if they would like, and assist them in connecting to a higher level of care if needed (e.g., by providing mental health referrals).

Participants will be provided with an outline of resources for accessing mental health care at the completion of the study.

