## VI. BIOSTATISTICAL ANALYSIS

### a. Specific data variables being collected for the study

The primary outcomes are feasibility and acceptability of the intervention and research procedures (Table 1). Study staff will record all feasibility outcomes throughout recruitment, screening, enrollment, and the intervention, data collection, and follow-up phases.

Table 1. PRIMARY OUTCOMES	
Feasibility	
Recruitment	$\geq 70\%$ consent to screening; $\geq 70\%$ meet screening criteria; $\geq 70\%$ of eligible enroll; enroll $\geq 20$ participants/month
Eligibility criteria	$< 20\%$ ineligible due to each criterion; reasons for ineligibility; reasons for refusal; characteristics of refusers
MBCT and control interventions	Adherence: $\geq 75\%$ session attendance; retention: $\geq 75\%$ post-assessments, $\geq 70\%$ follow-up assessments completed; fidelity: checklist score $\geq 80\%$ ; $\geq 75\%$ complete home practice at least 3 days/week
Videoconferencing	$< 20\%$ of connections dropped during session; $< 20\%$ of sessions missed due to technical problems; number ( $M < 2.0$ ) and type of problems; $< 20\%$ ask for extra training, type of extra training needed
Blood spots	Adherence: $\geq 75\%$ submitted at baseline, post-intervention, $\geq 60\%$ submitted at follow-up; 80% adequate quality
Acceptability	
MBCT and control interventions	Session satisfaction and helpfulness, enjoyment, relevance, utility of each session component (1=not at all, 10=very much; $M \geq 7.5$ ; post-session survey ); overall program satisfaction ( $M \geq 7.5$ ), $\geq 75\%$ plan to use the skills, $\geq 75\%$ would recommend the program to others ( post-intervention )

	survey); likes, dislikes, suggestions for improvement (exit interview); <math>\geq 60\%</math> continue meditation practice (follow-up survey)
Videoconferencing	Ease and confidence of use (1=not at all, 10=extremely <math>M \geq 7.5</math>), interference of technical problems (1=none, 10=extreme; <math>M < 2.0</math>), audiovisual quality and overall satisfaction (1=poor, 10=excellent; <math>M > 7.5</math>; post-session survey); pros and cons, suggestions for improvement (exit interview)

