**Aim 2. Exploratory outcomes.** As a pilot feasibility trial, I will explore within-group changes in emotional, physiological, and health behavior variables from before to after the intervention. I will examine frequency distributions for all variables and use non-parametric tests if needed. I plan to use linear mixed effects models with repeated measures and an unstructured covariance matrix to assess changes within the MBCT and control group for the following dependent variables: depression symptoms, inflammation, emotion regulation, pro-sociality, health behaviors, and cardiac health (Table 2). The predictor variables will be time (fixed effect; two levels: baseline, post-intervention) and covariates relevant for each dependent variable (random effects; section 5.1). I will explore follow-up outcomes in separate models where time is a fixed effect (three levels: baseline, post-intervention, follow-up) and covariates are included as random effects, with pairwise comparisons between follow-up and the other two time-points. I will explore correlations between changes (post-intervention minus baseline) in depression symptoms and inflammation, emotion regulation, pro-sociality, and health behaviors. For dropouts, I will impute missing data using maximum likelihood estimation and, as a sensitivity analysis, the last observation carried forward. For all analyses, trends will be considered based on a two-tailed  $\alpha=.10$ .

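### The plan does not separate leaving the study for worsening from ending assessments, so PHQ-9 change may be informatively missing in those who deteriorate

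*Combined protocol and SAP*

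**What the plan says.** Section VII.d (Psychosocial risks) names worsening depression and suicidal ideation as the main psychosocial safety concern. It sets out two responses to worsening during the study:

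- Removal: "The objective criteria for removal from the study is worsening psychiatric symptoms that become psychiatrically unstable that precludes their participation".
- For worsening that does not require removal, the PI discusses the concern with the participant and will "give them the option to exit the study if they would like, and assist them in connecting to a higher level of care if needed".

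The same section gives the scored monitoring: "For enrolled participants, the PHQ-9 will be administered at baseline, post-intervention, and 3-month follow-up, which will allow us to monitor for worsening depression symptoms". During the eight weeks of sessions the monitoring is by observation: "The interventionists for each group will observationally monitor participant's symptoms during each weekly intervention session".

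Section VI.c (Statistical methods) deals with missing outcomes in one sentence: "For dropouts, I will impute missing data using maximum likelihood estimation and, as a sensitivity analysis, the last observation carried forward". PHQ-9 change is an exploratory, within-group outcome (Section VI.a, Table 2). Retention is a primary feasibility outcome (Table 1), with benchmarks of at least 75% of post-intervention assessments and at least 70% of follow-up assessments.

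**The concern.** Both responses are worded as leaving the study. Nothing in the protocol says whether a participant who stops sessions because of worsening is still asked to complete the post-intervention and 3-month surveys. The plan does make this kind of distinction elsewhere. Section VII.a keeps participants who decline the blood spots in all other procedures, and Section VII.d lets participants skip surveys or items. No similar sentence covers those who stop because they have worsened.

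If leaving the study ends the assessments, the PHQ-9 is missing because of the very thing it measures. Maximum likelihood assumes that, given the observed data, missingness does not depend on the unseen score. LOCF from baseline assumes no change. For these participants both assumptions err in the favourable direction. At stake is whether the pilot, which Section VIII.b says will inform a later efficacy trial, can show how many people deteriorated, by how much and in which arm.

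**Working it through.** **No figure to reproduce.** Section VI.d reports no power analysis. The documents give no expected removal rate, PHQ-9 change or standard deviation, so the arithmetic below is an illustration on assumed values.

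**Step 1. Who loses a score.** The only PHQ-9 time points after enrolment are baseline, post-intervention and 3 months (Sections V.a and VII.d). The weekly post-session surveys cover likes and dislikes of session components (Section V.a).

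- Leaves before the post-intervention survey: no post-baseline PHQ-9, if leaving ends assessments.
- Worsening first seen at the post-intervention survey: that score is recorded and enters the baseline-to-post model. Only the 3-month score can be lost.
- Worsening first seen at 3 months: all three scores are recorded.

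The problem is therefore mainly with the first group.

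**Step 2. Bias in the arm mean.** Let n be the number per arm, k the number who leave for worsening before the post score, m the mean change in those who stay and w the change in those who leave.

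- True mean change = [(n - k)m + kw] / n
- Likelihood estimate ≈ m, if baseline scores and covariates do not predict who leaves
- LOCF estimate = (n - k)m / n, because baseline is carried forward as zero change
- Overstatement of improvement: k(w - m)/n under likelihood, kw/n under LOCF

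Assume n = 20 (N=40 in Section VI.d, 1:1), m = -3 and w = +6:

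| k | True mean | Likelihood | LOCF | Overstatement, likelihood | Overstatement, LOCF |
|---|---|---|---|---|---|
| 1 | (19 × -3 + 6)/20 = -2.55 | -3.00 | -57/20 = -2.85 | 0.45 | 0.30 |
| 2 | (18 × -3 + 12)/20 = -2.10 | -3.00 | -54/20 = -2.70 | 0.90 | 0.60 |
| 3 | (17 × -3 + 18)/20 = -1.65 | -3.00 | -51/20 = -2.55 | 1.35 | 0.90 |

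**Step 3. Sensitivity.** Section II.a gives about 50 participants rather than 40, so both sizes are shown. With k = 2, m = -3 and w = 3, 5 or 8:

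- n = 20: 0.60, 0.80, 1.10 under likelihood; 0.30, 0.50, 0.80 under LOCF.
- n = 25: 0.48, 0.64, 0.88 under likelihood; 0.24, 0.40, 0.64 under LOCF.

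The direction is the same throughout. The size depends on the assumptions.

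**Step 4. Could it happen at all?** The chance of at least one removal in the trial is 1 - (1 - p)^N. For assumed p of 1%, 2%, 5% and 10% it is 33%, 55%, 87% and 98.5% with N = 40, and 40%, 64%, 92% and 99.5% with N = 50.

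**Step 5. Would the retention outcome reveal it?** With 20 per arm, 75% is 15, so an arm with up to 5 missing post-intervention assessments still meets the benchmark. Three departures for worsening could sit within a benchmark that is met. Table 1 asks for reasons for ineligibility and refusal, not for removal or exit. Section VI.c compares adherent and non-adherent participants on baseline variables only.

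**The case against.** The strongest reply is that the protocol never says assessments stop. A reader might infer from the wording that PHQ-9 follow-up ends by rule once someone is removed, but that rests on the phrasing and on silence. The consent form and the standardized safety assessment protocol, which might settle it, are mentioned but not reproduced. This stands. The defect is that the plan does not state what happens, and that its literal wording points towards loss of the data.

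A reader might also infer that worsening in these participants never reaches the results. The documents do not support that. Worsening found at a scheduled survey is recorded, departures count against retention, and adverse events that staff learn of go to the PI for review (Sections IX.b and IX.d). What remains is that a departure counted in retention carries no required reason, and neither outcome table reports departures for worsening by arm.

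Nor can one conclude that safety contact is abandoned. Section VII.d provides for a call after the session, safety assessment, PI contact, notice to treating providers, referral and a prior emergency plan. The exit offer for lesser worsening is voluntary and repeats a right that every participant has. These points stand too. Such contacts serve care and do not yield a PHQ-9 score for analysis.

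Finally, the numbers are assumed, and the plan itself expects few such cases. It describes active suicidality needing intervention as extremely rare in the team's previous work and does not expect a severely depressed sample. PHQ-9 change is exploratory in a pilot whose primary outcomes are feasibility and acceptability. This limits the consequence but does not remove the gap.

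**Conclusion.** The point holds as a gap in the plan with a predictable direction of bias. Removal and exit for worsening are framed as leaving the study, nothing keeps those participants in assessment, and the two planned missing-data methods would make the within-group PHQ-9 change look better than it was for anyone lost before the post-intervention survey.

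The size cannot be known from the documents. On the assumed values in Step 2 the overstatement is 0.45 to 1.35 points under likelihood and 0.30 to 0.90 under LOCF for 1 to 3 departures in an arm of 20. These figures require that all departures precede the post-intervention survey, that leaving ends assessment and, for likelihood, that nothing observed at baseline predicts who leaves. If departures are rarer or the worsening smaller, the effect shrinks in proportion.

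The primary feasibility conclusions are little affected. The change is worth making because the pilot's description of harm by arm depends on it.

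**What to change.** Leave the clinical criterion for removal and the team's discretion over it exactly as they are. Change only what is said about assessments and reporting:

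1. In Section VII.d, state that stopping the group sessions does not by itself end the planned post-intervention and 3-month surveys, with the PHQ-9 as the minimum, unless the participant declines or the PI judges contact inappropriate. Section V.a already allows surveys by phone.
2. Record the reason for each removal or exit, and whether it was from sessions only or also from assessments.
3. Report by arm the number who stopped sessions or left the study for worsening symptoms, next to retention and the PHQ-9 results, so that the likelihood and LOCF estimates can be read with that number in view.

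The cost is minor protocol and consent wording, and at most two survey contacts per affected participant that are already planned. Some will decline the later surveys, so the gap will narrow rather than close. The count by arm is useful even then.

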**e. Radiation risks**

There are no radiation risks associated with this study.

## **VIII. POTENTIAL BENEFITS**

**a. Potential benefits to participating individuals**

Participants may not benefit from this study. It is hoped that the intervention will result in improved scores on depression symptom measures. The current study may provide training in coping skills for managing depression and improving health behaviors, and promote understanding of depression and cardiac health. It may also provide emotional benefits for participants to share and receive support with their peers and a trained clinician.

**b. Potential benefits to society**

Developing targeted, efficacious, and accessible interventions to treat depression in ACS patients may have important public health benefits. Depression is common and deadly among acute ACS patients with up to 45% experiencing at least mild depression symptoms. Even mild depression symptoms double the risk of death in ACS patients. Mind-body interventions that are accessible and address the underlying pathophysiology of comorbid depression and cardiovascular disease are needed, and the MBCT intervention being tested in the current study has the potential to address this need. This study will establish the feasibility and acceptability of the intervention and inform targets for refinement in a future R01 efficacy trial. Thus, participation in this study may result in the development of an innovative, efficacious, and accessible depression treatment that can have substantial benefit to future ACS patients.

## **IX. MONITORING AND QUALITY ASSURANCE**

**a. Independent monitoring of source data**

Source materials will include information collected from survey questionnaires at baseline, post-intervention, and 3-month follow-up; exit interviews; weekly practice logs; post-session surveys; and blood spot collection procedures. All self-

report questionnaires will be entered electronically via REDCap. Individual exit interviews will be conducted by phone or videoconferencing. Upon their receipt, all dried blood spot samples will be stored securely in an MGH affiliated lab, on the MGH campus. Samples will later be shipped, in accordance with MGB and CDC guidelines, to our collaborators [name] and [name] at Northwestern University for storage and/or processing. All samples will be labeled with the patient ID, date of collection, group assignment, and time point (baseline, post-intervention, 3-month follow-up). We will follow all CDC shipping guidelines (e.g., placing a freeze pack inside of an insulated shipping container, placing sealed plastic bags containing the samples into a box). We will seal the box tightly with tape and ship specimens via courier to [name] in Health Lab at the Northwestern University Feinberg School of Medicine.

[name] will securely store the samples in his locked lab at Northwestern before bringing them for processing to his collaborator [name] at the Laboratory for Human Biology Research at Northwestern University. The blood samples will not contain identifiers that could be used by the outside collaborators to link the data to individual subjects; they will be labeled with participants' study ID numbers and not any personally-identifying information, and only Partner's study staff will have access to the data file linking participant's personal information to their study ID number. Study staff have completed CDC and HealthStream trainings on dried blood spot storage and shipping and have acquired the proper documentation to ship samples to a non-MGB lab.

All information collected will be for the purposes of research and will only be accessible to study staff and stored securely on the Partners' network. Survey and practice log data will be reviewed for completeness though participants will be allowed to skip any questions they are not comfortable answering.

